8.5.3. BCRP Inhibitors

A primary objective of this study is to assess the effect of osimertinib on the PK of G1T38 via the mechanism of BCRP inhibition by osimertinib. Therefore, patients are prohibited from taking drugs, herbal supplements, or foods that are strong BCRP inhibitors during participation in this study (beginning 14 days prior to the first dose of study drug until 14 days after last dose of study drug).

• **Prohibited, strong inhibitors of BCRP**, including but not limited to the following: sulfasalazine, curcumin, turmeric supplements, cyclosporine, eltrombopag

8.5.4. BCRP substrates

Patients taking concomitant medications whose disposition is dependent upon BCRP and which have a narrow therapeutic index should be closely monitored for signs of changed tolerability as a result of increased exposure of the concomitant medication while receiving osimertinib. Guidance on medications to avoid, medications that require close monitoring, and on washout periods is provided in the appendices.

Patients taking rosuvastatin should have creatine phosphokinase levels monitored (due to BCRP-mediated increase in exposure). If the patient experiences any potentially relevant AEs suggestive of muscle toxicity including unexplained muscle pain, tenderness, or weakness, particularly if accompanied by malaise or fever, rosuvastatin must be stopped and any appropriate further management should be taken.

8.5.5. Gastric pH Elevating Agents

The solubility of G1T38 is pH dependent. Drugs that raise gastric pH may alter the bioavailability of G1T38 and confound the interpretation of PK data. During Part 1 of the study, concurrent use of medications that raise gastric pH is **prohibited** from 7 days prior to first dose of study drug until after the final PK sample is collected on Cycle 1 Day 1. Such medications include proton pump inhibitors (eg, omeprazole, pantoprazole, lansoprazole, esomeprazole, rabeprazole, dexlansoprazole), H2 blockers (eg, nizatidine, famotidine, cimetidine, ranitidine), and antacids (eg, sodium bicarbonate, calcium carbonate, aluminum-based antacids, magnesium compounds, alginic acid).

8.5.6. CYP2C8 Inhibitors and Inducers

G1T38 is a substrate for CYP2C8, although the extent of metabolism by CYP2C8 is expected to be low in humans since the in vitro clearance of G1T38 in human liver

microsomes and hepatocytes was low. G1T38 exposure may be altered by concomitant use of drugs, herbal supplements, or foods that are strong CYP2C8 inhibitors or inducers.

- Caution should be exercised with concomitant use of drugs that are strong inhibitors of CYP2C8 (eg, gemfibrozil, quercetin, sulfinpyrazone, trimethoprim, and nicardipine).
- Caution should be exercised with concomitant use of drugs that are strong or moderate inducers of CYP2C8 (eg, rifampin, phenobarbital, and carbamazepine).

8.6. Systemic Corticosteroid Use

Steroids given for physiological replacement (up to 10 mg per day of prednisone or equivalent), as anti-emetics, or by inhalation, ophthalmic, or topical route are allowed. Short courses (up to 21 days) of steroids are allowed to treat acute conditions if medically necessary.

8.7. Supportive Care for Gastrointestinal Adverse Events

Medications to treat gastrointestinal AEs are allowed at any time during the study, as indicated (eg, loperamide for diarrhea, 5-HT3 antagonists for nausea/vomiting, etc.). Such medications shall not be used as primary prophylaxis prior the onset of any gastrointestinal AEs. After a patient has experienced a gastrointestinal AE, supportive treatments may be used as secondary prophylaxis if the patient continues to experience the AE.

8.8. Additional Cautions

G1T38 inhibited P-gp, BCRP, MATE1, MATE2-K, and OCT1 and 2 membrane transporters and therefore caution should be exercised with concomitant use of drugs that are substrates for these transporters (Section 4.2.2; Appendix 4). MATE2-K is involved with tubular secretion of creatinine and inhibition of MATE2-K by G1T38 may cause an increase in serum creatinine levels unrelated to true changes in renal function.

G1T38 is a substrate and inhibitor of P-gp and BCRP efflux transporters. G1T38 exposure may be altered by concomitant use of drugs that are strong inhibitors or inducers of P-gp or BCRP. Caution should be exercised with concomitant use of drugs that are strong inhibitors or inducers of P-gp. Use of strong inhibitors of BCRP during participation in this study is prohibited.

The use of herbal medicine or traditional remedies is not recommended during the active treatment phase.

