10.6.2. Clinical Laboratory Assessments

Blood samples will be collected for clinical laboratory assessments as outlined in Table 9-1 (Part 1) and Table 9-2 (Part 2). Hematology, clinical chemistry, and urinalysis samples may be obtained up to 48 hours prior to the scheduled visit. If screening hematology, clinical chemistry, and urinalysis assessments have been performed within 7 days of Cycle 1 Day -16 for Part 1 or within 7 days of Cycle 1 Day 1 for Part 2, then these tests do not have to be repeated prior to commencing first treatment with study drug as long as the patient's clinical condition has not changed. After baseline assessment (Day -16 in Part 1, Cycle 1 Day 1 in Part 2), Cystatin C shall be evaluated only in the event that the serum creatinine is elevated. The measurement of Cystatin C to estimate glomerular filtration rate is included in this study because G1T38 may inhibit MATE transporters in the renal tubule and induce a nonpathologic increase in serum creatinine. The clearance of Cystatin C is not dependent upon the MATE transporters and thus can help differentiate the effect of G1T38 on the MATE transporter from a true decline in renal function.

Absolute neutrophil counts will be monitored weekly for the first 8 weeks (2 cycles), then every 2 weeks for the next 2 cycles. Beginning with Cycle 5 Day 1, patients with stable ≤ Grade 2 hematologic parameters may have hematology monitored monthly on Day 1 of each cycle; patients that do not meet this criteria will continue to have every other week assessment of hematologic parameters.

Clinical chemistry will be monitored every 2 weeks for the first 4 cycles. Beginning with Cycle 5 Day 1, clinical chemistry will be monitored monthly on Day 1 of each cycle.

Clinical laboratory tests to be performed are presented in Table 10-5.

Table 10-5 Clinical Laboratory Tests

Hematology Hemoglobin Hematocrit WBCs with differential Platelets	Chemistry Albumin Alkaline phosphatase Total bilirubin Calcium Chloride Creatinine Glucose Inorganic phosphorus	Potassium Total protein ALT AST Lactate dehydrogenase Sodium Blood urea nitrogen/urea Cystatin C ^a
Urinalysis Specific gravity pH Glucose Protein Bilirubin Ketones Leukocytes Hemoglobin Microscopic examination (including RBC, WBC, and casts will be performed, if necessary)	Pregnancy test Blood or urine tests are acceptable based on the site's standard clinical practice; applicable to women of childbearing potential only.	

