4.2.4. Laboratory

Blood and urine samples for determination of clinical chemistry, hematology, and urinalysis will be collected. The laboratory variables in [Table 8](#) will be measured.

G1 Therapeutics, Inc.
 Clinical Study Protocol G1T38-03
 Statistical Analysis Plan

Laboratory toxicities will be assessed using the NCI CTCAE, Version 4.03. Details on CTCAE grading criteria are presented in the Appendix Table A1. Change from baseline and percent change from baseline in laboratory test results to each assessment will also be derived.

Table 8 Clinical Laboratory Tests

Hematology	Chemistry	
Hemoglobin	Albumin	Potassium
Hematocrit	Alkaline phosphatase	Total protein
WBCs with differential	Total bilirubin	ALT
Platelets	Calcium	AST
	Chloride	Lactate dehydrogenase
	Creatinine	Sodium
	Glucose	Blood urea nitrogen/urea
	Phosphorus	Cystatin C ^a
Urinalysis	Pregnancy test	
Specific gravity	Blood or urine tests are acceptable based on the site's standard clinical practice; applicable to women of childbearing potential only.	
pH		
Glucose		
Protein		
Bilirubin		
Ketones		
Leukocytes		
Hemoglobin		
Microscopic examination (including RBC, WBC, and casts will be performed, if necessary)		

ALT = alanine aminotransferase; AST = aspartate aminotransferase; RBC = red blood cell; WBC = white blood cell

^a Postbaseline Cystatin C to be evaluated in the event that serum creatinine is elevated, if it is available as a local test

Collected serum calcium will not be summarized in tables, instead, corrected serum calcium will be derived from calcium and albumin results based on the following formula:

$$\text{Corrected Calcium} = \text{Calcium (mmol/L)} + 0.02 (40 - [\text{Albumin}] (\text{g/L}))$$

Laboratory Values with < or > Inequality Symbols

Some continuous laboratory data include “<” or “>” symbols. Data will be presented in listings with their inequality symbol; however, for tabulation of summary statistics of safety laboratory results, the given numeric value will be used in the summary statistics, ignoring the nonnumeric qualifier.

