5. ANALYSIS METHODS (PART 1)

5.1 General Principles

5.1.1. General Statistical Considerations

All statistical analyses will be performed using SAS® Version 9 or higher.

Data will be summarized descriptively by dose level and overall.

G1 Therapeutics, Inc.
Clinical Study Protocol G1T38-03
Statistical Analysis Plan

The descriptive summary for the categorical variables will include counts and percentages. The descriptive summary for the continuous variables will include mean, median, standard deviation (SD), and minimum and maximum values. The descriptive summary statistics of time to first objective response will include median, 25% and 75% percentiles, and minimum and maximum values. The Kaplan-Meier method will be used to estimate the probability of survival (PFS and DOR) and the respective the time-to-event percentiles.

In general, the precision of descriptive statistics for continues variables min and max will always be consistent with the precision of the variable of summarization. Additional rounding rules are listed as follows:

- If the original value has <= 1 decimal places, mean and median will have one more decimal as the original value. Measures of variability (e.g, SD will be rounded two more decimal places than the precision of the original measure.
- If the original value has two decimal places, mean and median will have the same decimal places as the original value. Measures of variability will be rounded one more decimal place than the precision of the original measure.
- If the original value has >2 decimal places, all the descriptive statistics will have the same decimal places as the original value.

For categorical variables, non-zero percentages will be displayed with 1 decimal place, zero-percentage will not be displayed. A percentage value less than 0.1% will be displayed as “<0.1%.” A percentage value less than 100% but greater than 99% will be displayed as “>99%.”

Part 1 of the study is descriptive in nature. No formal statistical test will be conducted. Two-sided 95% exact CI will be provided for tumor response rate by using Clopper-Pearson method. 95% CI will be provided for PFS percentiles by using log-log transformation approach.

Any rounding will be done after all calculations are made.

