ECOG performance status will be summarized using descriptive statistics at each scheduled visit during the treatment period. Number and percentage of patients will be summarized for each status. In addition, the maximum post-baseline performance status during treatment period will be presented, including assessment at unscheduled visits.

ECOG performance status (0, 1, 2, 3, 4, and 5) will be listed.

Electrocardiograms

ECG parameter (e.g., QT interval corrected by Fridericia's formula [QTcF]) observed values and changes from Baseline will be summarized using descriptive statistics for each scheduled visit, last assessment during treatment period and maximum and minimum post-baseline during treatment period. Both scheduled and unscheduled assessments will be used to identify last and worst post-baseline values during treatment period. For the triple assessments as a specific time point, the average will be summarized for that time point.

Incidence of ECG meeting potentially clinically significant criteria ([Table 9](#)) will be summarized with frequencies and percentages.

An accompanying listing of subjects will be produced and it will display all ECG measurements collected on CRF together with derived values (RR, QTcB and QTcF) and findings during the study in subjects with abnormal ECGs, as determined by the investigator.

Laboratory Results

For the purposes of summarization in both the tables and listings, all laboratory values will be converted and presented in SI units.

Clinical laboratory parameters observed values, changes from Baseline, and percent changes from Baseline will be summarized using descriptive statistics for each scheduled visit, last value during treatment period, maximum and minimum post-baseline value during treatment period. Last value during treatment period, maximum and minimum values will be based on both scheduled and unscheduled visits. Graphical presentations of median and change from baseline over time will provide additional focus to be placed on absolute neutrophil count.

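### The SAP averages cystatin C by visit although after baseline it is measured only when creatinine is high, and no planned summary pairs the two tests

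*Protocol*

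**What the plan says.** **Purpose.** Protocol 10.6.2 says that "G1T38 may inhibit MATE transporters in the renal tubule and induce a nonpathologic increase in serum creatinine" and that cystatin C "can help differentiate the effect of G1T38 on the MATE transporter from a true decline in renal function". Protocol 8.8 gives the same warning about creatinine: "inhibition of MATE2-K by G1T38 may cause an increase in serum creatinine levels unrelated to true changes in renal function". Both sections state the transporter effect as a possibility.

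**Sampling.** Table 9-1 schedules cystatin C for all Part 1 patients on Day -16 and afterwards only when serum creatinine exceeds ULN. Protocol 10.6.2 agrees: after baseline, "Cystatin C shall be evaluated only in the event that the serum creatinine is elevated". The footnote to SAP Table 8 (4.2.4) narrows this further: "Postbaseline Cystatin C to be evaluated in the event that serum creatinine is elevated, if it is available as a local test".

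**Analysis.** SAP Table 8 lists cystatin C among the routine chemistry tests. SAP 5.2.10 then states: "Clinical laboratory parameters observed values, changes from Baseline, and percent changes from Baseline will be summarized using descriptive statistics for each scheduled visit". It adds last, maximum and minimum on-treatment values and makes no exception for cystatin C. SAP 5.1.1 fixes the statistics: "The descriptive summary for the continuous variables will include mean, median, standard deviation (SD), and minimum and maximum values". SAP 5.1.2 does not impute missing laboratory values. SAP section 4 computes change from baseline only where both values exist.

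**Grades.** SAP 5.2.10 also plans CTCAE shift tables and treatment-emergent worst-grade tables. It gives some tests special treatment: corrected calcium replaces calcium in tables, neutrophils get graphs, and Hy's law cases get a listing. Cystatin C, whose post-baseline sampling depends on another result, gets none.

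**The concern.** Creatinine and cystatin C both rise when filtration falls. Measuring cystatin C only where creatinine is high therefore favours patients whose filtration is lower than average, either always or on that day. Two comparisons in the by-visit table are affected.

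- **Observed values.** The baseline row averages everyone and later rows average the selected few. Stable differences between patients are enough to make the later mean higher.
- **Change from baseline.** Pairing removes the stable differences. What remains is selection on visit-to-visit variation.

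A reader of the by-visit table could see cystatin C rising on treatment when average renal function has not moved. The graded creatinine tables cannot settle the matter, because a creatinine grade looks the same whether it comes from transporter inhibition or from lost filtration. Cystatin C is collected to make that distinction, but the SAP describes no summary in which the two tests are read together.

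**Working it through.** **Figures in the documents.** There is no stated figure for this point to reproduce. The only related count is creatinine-increased adverse events in Study G1T38-02 (Protocol Table 4-1): 2/18 = 11.1%, all Grade 1-2.

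**Inputs assumed, none from the documents** (log scale): stable between-patient SD of filtration b = 0, 0.15 or 0.25; within-patient SD w = 0, 0.05 or 0.10; other stable determinants, SD 0.15 for creatinine and 0.10 for cystatin C; measurement SD 0.05 and 0.08 respectively; ULN 35% above the typical creatinine; transporter rise in creatinine r = 0%, 15% or 30%. True mean change in filtration is set to zero.

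**Model.** Cystatin C is observed at a visit only if log creatinine exceeds ln 1.35. Let s² = b² + w² + 0.15² + 0.05² and d = ln 1.35 − ln(1 + r), with Φ the normal distribution function. Then:

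- share sampled = Φ(−d/s)
- observed-value mean relative to all-patient baseline = Φ((b² + w² − d)/s) / Φ(−d/s)
- mean paired ratio = exp(w² + 0.08²) × Φ((w² − d)/s) / Φ(−d/s)

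**One case by hand** (b = 0.15, w = 0.05, r = 15%): s² = 0.0225 + 0.0025 + 0.0225 + 0.0025 = 0.05, so s = 0.2236; d = 0.3001 − 0.1398 = 0.1603.

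- Sampled: Φ(−0.717) = 0.237.
- Observed: Φ(−0.605)/0.237 = 0.2726/0.2367 = 1.151, or +15.1%.
- Paired: exp(0.0089) × 0.2402/0.2367 = 1.024, or +2.4%.

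**Simulation, 400,000 patients per case.** Cells give the apparent rise in observed mean / mean paired change, in percent.

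| b, w | r = 0% | r = 15% | r = 30% |
|---|---|---|---|
| 0, 0 | +0.1 / +0.4 | −0.1 / +0.6 | 0.0 / +0.6 |
| 0, 0.10 | +11.5 / +13.3 | +7.7 / +9.5 | +5.0 / +6.8 |
| 0.15, 0.05 | +21.7 / +2.9 | +15.1 / +2.4 | +10.3 / +2.0 |
| 0.25, 0 | +35.9 / +0.7 | +26.0 / +0.6 | +18.7 / +0.7 |
| 0.25, 0.10 | +38.7 / +6.7 | +28.1 / +5.4 | +20.5 / +4.5 |

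Over all 27 combinations the observed-value rise runs from about 0% to +39% and the paired change from +0.4% to +13.3%. If everyone were sampled, the observed mean would move by 0.0% and the paired change would be +0.6% to +1.7%, which is ratio noise only.

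By within-patient SD, the paired change is about +0.6% at w = 0, +1.6% to +4.2% at w = 0.05, and +4.5% to +13.3% at w = 0.10. In every row where filtration varies, the observed-value rise falls as r grows.

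**How many values per visit.** Taking 11.1% as an illustrative trigger rate (it is an adverse-event rate, not a rate above ULN), the expected number is 6 × 0.111 = 0.7, 18 × 0.111 = 2.0 or 36 × 0.111 = 4.0. The chance of at least two values is 14%, 61% and 92%. Most by-visit cystatin C means within a dose level would rest on very few patients.

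**The case against.** The strongest reply has four parts.

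1. **The paired change is true for the patients measured.** They do have somewhat lower filtration at that visit, and the error comes only from generalising to everyone. This stands for the change column. It does not help the observed-value column, where the distortion is larger.
2. **The size is a product of assumptions.** This stands. If filtration is stable within patients, the paired bias vanishes; if it does not vary between patients either, so does the observed-value bias. A within-patient SD of 0.10 gives the upper part of the paired range and should not be read as typical.
3. **Listings already do the job.** SAP 5.2.10 lists laboratory values by subject with out-of-range flags, and Part 1 has at most 36 patients. A careful reader could pair the values by hand. This lowers the severity, but the by-visit summary would still mislead and no described summary would correct it.
4. **A paired display may exist elsewhere.** Grading criteria are deferred to Appendix Table A1 and layouts to separate shells, neither of which was available here. That is why the point is limited to what the SAP text describes.

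A reader might also infer that the SAP reports a known transporter effect as renal toxicity. The documents do not support this. The protocol says only that the drug may act in this way, and the SAP uses the general CTCAE word toxicities for all laboratory grades without calling creatinine grades renal. Nor do the two displays reinforce each other. The larger the transporter effect, the more the creatinine tables could mislead, but the less the cystatin C mean is shifted.

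**Conclusion.** The point holds as a minor fault of presentation. By-visit cystatin C means mix an all-patient baseline with later values from patients selected on a correlated marker. The distortion lies mainly in the observed-value column: about 0% to +39% under the stated assumptions, against about +0.5% to +13% in paired change. The direction follows from the sampling rule whenever the two markers share variation in filtration; the size rests wholly on assumed inputs. Separately, the creatinine grade tables cannot tell a possible MATE effect from a fall in filtration, and the SAP text plans no summary that uses cystatin C to do so.

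Because Part 2 will not be conducted, a reader might infer that these tables become the renal safety conclusion for the combination. That goes too far: adverse events, urea and urinalysis also bear on renal safety. Part 1 is descriptive, and no test, primary endpoint or dose decision is shown to depend on the cystatin C mean.

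**What to change.** In SAP 5.2.10:

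1. Remove post-baseline cystatin C from the by-visit observed-value and change summaries. Alternatively, show it only with n and against the Day -16 values of the same patients.
2. Add one patient-level table or listing beside the creatinine shift table. It covers patients with creatinine above ULN or a treatment-emergent creatinine grade, and classifies same-visit cystatin C as raised, not raised (against both ULN and the Day -16 value) or not done. The last category matters because the SAP makes the test depend on local availability.

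This needs SAP wording and one small display from data already collected, with no new sample or visit. The drawback is few patients per cell, so the display should be read as individual cases rather than as rates.

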8.9. Concomitant Radiotherapy or Surgery

Palliative radiotherapy is not allowed within the DLT period. In Part 1 (after the DLT period) and in Part 2, palliative radiotherapy may be permitted to control symptoms (eg, treatment of painful bony lesions or brain or thoracic lesions) provided that the lesions were known to be present at the time of study entry and the investigator clearly documents that the need for palliative radiotherapy is not indicative of disease progression. Refer to Appendix 6 for additional guidelines on radiotherapy.

Any diagnostic, therapeutic, or surgical procedures performed during the study period shall be documented.

8.10. Contraception

Females

All females of childbearing potential must have a negative serum beta human chorionic gonadotropin (β -hCG) test result at screening and not be breastfeeding prior to start of dosing.

Females must be either postmenopausal, surgically sterile, or agree to use 2 forms of highly effective contraception from the start of the study until 4 months after discontinuation of study drug.

Highly effective methods of contraception are those that result in a low failure rate (ie, less than 1% per year) when used consistently and correctly. These include the following:

- Established use of oral, injected, or implanted hormonal methods of contraception (stable dose at least 3 months prior to dosing)
- Placement of an intrauterine device or intrauterine system
- Barrier methods of contraception: condom or occlusive cap (diaphragm or cervical/vault caps) with spermicidal foam/gel/film/cream/suppository. Barrier methods alone (without spermicide) are not acceptable methods. Likewise, spermicide alone is not an acceptable method.
- Male sterilization (with the appropriate post vasectomy documentation of the absence of sperm in the ejaculate). For female patients on the study, the vasectomized male partner should be the sole partner for that patient.

True abstinence, when this is in line with the preferred and usual lifestyle of the patient. Periodic abstinence (eg, calendar, ovulation, symptothermal, postovulation methods) and withdrawal are not acceptable methods of contraception.

Postmenopausal is defined as meeting 1, 2, or 3 below:

- 1. At least 60 years of age and amenorrheic for at least 12 months following cessation of all exogenous hormonal treatments OR
- 2. Medically confirmed ovarian failure OR
- 3. Younger than 60 years of age **and** have had cessation of regular menses for at least 12 consecutive months with no alternative pathological or physiological cause **and** have serum levels of estradiol and follicle stimulating hormone within the laboratory's reference range for postmenopausal females

Acceptable surgical sterilization techniques are complete or partial hysterectomy or bilateral tubal ligation with surgery at least 6 months prior to dosing, and bilateral oophorectomy with surgery at least 2 months prior to dosing.

Males

If male and sexually active, a condom, with spermicide, must be used with all partners from the start of the study until 4 months after discontinuation of study drug, or must be vasectomized. Patients should refrain from donating sperm from the start of dosing until 4 months after discontinuation of study treatment.

